⁷Early Term visit is only applicable if a subject does not complete the study within 28 days after dose administration

⁸Limited physical exam and vital sign evaluations will be completed if early termination occurs within 28 days after dose administration

⁹Sample aliquoted for vaccine virus detection (qPCR & infectivity)

¹⁰ Specifically includes the nares (including edema), throat, and lungs (including evaluation for wheezing). A targeted physical examination may be performed on other body systems if indicated based on review of interim medical history or subject symptoms as observed by site or by PI.

¹¹ Dispense/Review/Collect for 7 days following each dose administration including day of dosing

¹² Sample aliquoted for secretory IgA immune response

¹³ Sample collected if subject presents with AE

¹⁴ Sample may be tested for respiratory pathogens

¹⁵ Collected from PBMC processed blood

¹⁶ Blood pressure will be measured from the subject's arm after the subject has been at rest (seated or semi-recumbent) for approximately 5 minutes with the arm supported at the level of the heart. Blood pressure will be recorded to the nearest mmHg. Height and weight will be measured only at the screening visit.

¹⁷ Optional PBMC collection (Days 4 and 32) at select sites based on subject consenting on Day 4 and/or Day 32

¹⁸ PBMC and plasma collected at select sites for ~160 subjects

¹⁹ During the treatment period (Day 1 – Day 57), subjects will be asked to notify the site immediately if symptoms of influenza (fever, chills, sore throat, rhinorrhea, cough, muscle/body aches) occur. Subjects will be reminded at every scheduled visit and phone call, and in addition to visits and calls scheduled above (when increased influenza infections are being reported in the geographic region of the investigational site) will be contacted at Days 15±2, 21±2, 43±2, and 50±2 by phone or messaging. If influenza is suspected the subject will be asked to return to the site for laboratory confirmation of influenza using nasal swabs.

²⁰ Due to the COVID-19 pandemic, local governments may issue stay-at-home orders which prevent centers from conducting on-site Day 209 visits. This protocol allows for Day 209 visit to be a safety follow-up phone call.

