6.1.4. Early Termination Visit

Subjects who withdraw consent will be asked to attend the clinic for safety evaluation as described in Early Termination assessments.

Early Termination assessments should be completed within 7 (± 3) days of discontinuation for subjects who discontinue from the study. The following assessments are to be performed:

- Complete physical examination (neurological, rectal and gynecological exams do not need to be performed unless clinically indicated); a limited physical exam will be completed if early termination occurs within 28 days after dose administration
- Vital signs (height, weight, blood pressure, heart rate, and temperature)
- Collect blood for serum chemistry and hematology
- Urinalysis (dipstick)
- Symptom Memory Aid
- Nasal swab into buffer for mucosal IgA and virus shedding
- Collect blood sample for humoral immunogenicity assays (MNT and other serum assays)
- Collect blood sample for cellular immunogenicity assays (PBMC, ELISpot) – only for select sites
- Collect blood for gene expression (PBMC, plasma) – only for select sites
- Record concomitant therapy/AEs/SAEs

6.1.5. **Unscheduled Visits**

Unscheduled visits can be planned:

- To obtain additional information to ensure safety to the subject. Additional blood and urine samples may be taken at the discretion of the Investigator.
- To obtain a nasal swab for assessment of potential influenza infection.
- To assess, confirm, and follow-up on out-of-range clinical laboratory test, or vital sign values that will determine a subject’s eligibility, or in case of a positive drug screen.
- The result of the retest will be considered for subject eligibility.

Findings made during unscheduled visits should be reported in the eCRF.

6.2. **Study Assessments**

6.2.1. **Clinical Evaluations**

6.2.1.1. **Medical History**

A complete medical history will include a review of all major body systems. Significant past and present medical history will be obtained by interview during the screening visit.

6.2.1.2. **Concomitant Medications**

Details of prescription and over-the-counter medications (including vitamins) currently used will be recorded during the screening visit. Concomitant medications will be reviewed at each visit and any new medications will be documented on the eCRF.

6.2.1.3. **Demographics**

Demographics will be obtained during screening only. Demographics will include the age and race as described by the subject.

6.2.1.4. **Physical Examination**

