6.2.3. Adverse Events

Adverse events will be monitored continuously from first administration of IP treatment until study Day 57. At regular intervals during the study, subjects will be asked non-leading questions to determine the occurrence of any AEs. All AEs reported spontaneously during the course of the study will be recorded as well. Solicited and unsolicited signs and symptoms will be reported as AEs after review by the Investigator or designee, either separately using the corresponding Medical Dictionary for Regulatory Activities (MedDRA) terminology of the sign or symptom or combined using the appropriate term. For example, a subject who experiences dysuria with blood, WBCs, and bacteria in the urine would be recorded as having a urinary tract infection.

For detailed definitions and reporting procedures of AEs, see [Section 9](#).

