7.3. Study Halting Rules

Vaccination of subjects will be suspended until after review of safety data by the SRC if any of the following halting rules are met:

1. One or more subjects experience a Grade 4 AE, vital sign or laboratory AE that cannot be clearly attributed to another cause.
2. Three or more subjects within a single sentinel group or ten or more subjects within the expansion group experience the same Grade 3 AE, vital sign or laboratory AE that cannot be clearly attributed to another cause.
3. One or more subjects experiences a SAE assessed as related to IP.
4. One or more subjects has laryngospasm, bronchospasm, or anaphylaxis associated with the study product within 72 hours of product administration.

Any AE or SAE that falls into the above criteria for suspending or terminating the study (including the occurrence of **any** Grade 3 AE, vital sign or laboratory AE that cannot be clearly attributed to another cause) must be reported by the investigator to the Sponsor **immediately (within 24 hours)**.

In the case of halting rules being met, the SRC will be convened as quickly as possible. After review of the safety data the SRC will make a recommendation to the Sponsor whether to resume, suspend or terminate the study. The Sponsor will communicate a decision to suspend or terminate the study to the Investigators.

Subsequent review of serious, unexpected, and related AEs by the Medical Monitor, SRC, IRB, the Sponsor(s), or the FDA or relevant local regulatory authorities may also result in suspension of further trial interventions/administration of study product at a site. The FDA and study Sponsor(s) retain the authority to suspend additional enrollment and study interventions/administration of study product for the entire study, as applicable.

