7.4. Removal of Subjects from the Study

Subjects have the right to withdraw from the study at any time for any reason, including personal reasons. A subject can withdraw without giving a reason. The Investigator should however try to determine why a subject withdraws from the study and document the reason for withdrawal in the source documents and in the EDC system.

Subjects **may** be withdrawn from the study in the event of:

- Meeting any of the halting rules in [Section 7.3](#)
- A severe AE or serious AE (SAE);
- Difficulties in obtaining blood or other samples;
- Failure of the subject to comply with the protocol requirements or to cooperate with the Investigator.

Subjects **must** be withdrawn from the study in the event of:

- Withdrawal of consent
- Lost to follow-up
- Death
- Termination of the study by the Sponsor (described in [Section 7.2](#))
- For safety reasons, it being in the best interest of the subject that he/she be withdrawn, in the Investigator’s opinion;
- A positive pregnancy test (the subject or, if reported by a male subject, his female partner), or if the subject/partner is non-compliant with the contraception requirements (see [Section 4.1](#));
- Development of a medical condition that requires concomitant treatment with a prohibited therapy (see [Section 5.9.2](#));
- Breaking of the randomization code during administration of the study drugs. If the code is broken for safety reporting purposes, the subject may remain in the study; however, in such case subject and site staff will remain blinded to IP treatment.

The monitor and Sponsor will be informed in the event of a subject being withdrawn from the study. In case of withdrawal due to an SAE (for details on AE reporting see [Section 9.7](#)), the Sponsor should be notified within 24 hours; in case of withdrawal for other reasons; the Sponsor should be notified within 2 days from the event.

Subjects who are withdrawn from the study prior to completion of the scheduled study procedures for any reason (AE, withdrawal of consent, etc.) should be invited to complete the assessments as much as possible: as long as the subject consents, all relevant assessments of the day on which the subject withdrew from the study should be completed, at least those related to safety, and the subject should come for a safety follow-up visit 4 weeks after vaccination. In case of an AE, the appropriate follow-up will be done.

Subjects who are withdrawn from the study will not be replaced.

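### Table 3 takes early-termination safety labs only from subjects who present with an AE, while Protocol Section 6.1.4 lists them for every subject who discontinues

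*Protocol*

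**What the plan says.** Four places in the Protocol govern what happens when a subject leaves early.

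- **Table 3, footnote 13 (Section 6.1).** In the Early Term column, the hematology, chemistry and urinalysis rows carry the note "Sample collected if subject presents with AE". The rows for AEs, SAEs and medically attended AEs, concomitant medications, the Symptom Memory Aid and serum for antibody assays do not.
- **Section 6.1.4.** "Early Termination assessments should be completed within 7 (± 3) days of discontinuation for subjects who discontinue from the study". The list that follows includes "Collect blood for serum chemistry and hematology" and a dipstick urinalysis, with no AE condition. The 28-day limit appears only in the choice of examination: "a limited physical exam will be completed if early termination occurs within 28 days after dose administration".
- **Table 3, footnotes 7 and 8.** Footnote 7 restricts when the early-termination visit applies, by reference to completing the study and to 28 days from a dose. Footnote 8 ties the limited examination and vital signs to exit within 28 days of a dose.
- **Section 7.4.** Withdrawn subjects are to be invited to further assessments: "all relevant assessments of the day on which the subject withdrew from the study should be completed, at least those related to safety". In addition, "the subject should come for a safety follow-up visit 4 weeks after vaccination".

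Laboratory findings count in this trial. The first halting rule in Section 7.3 reads "One or more subjects experience a Grade 4 AE, vital sign or laboratory AE that cannot be clearly attributed to another cause". SAP Section 9.3 tabulates results by change from baseline and by maximum shift in grade, and SAP Section 8.5 imputes nothing.

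**The concern.** Safety is the primary objective, and this is the first human study of Sing2016 M2SR. Footnote 13 asks for an AE before taking the test that might reveal one. This is circular, because Protocol Section 9.1 counts laboratory abnormalities as AEs. The footnote also does not say whether an AE that has already resolved qualifies.

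If sites follow Table 3, a symptom-free abnormality in a subject who leaves goes unseen, and the exit values that do exist come only from leavers with an AE. If some sites follow Table 3 and others Section 6.1.4, laboratory data among leavers also differ by site for reasons unrelated to the vaccine.

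**Working it through.** The plan gives no figure on this point, so the check is mainly a comparison of texts. The arithmetic only shows scale.

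**1. The laboratory conflict.** Same visit, same three tests: Table 3 requires an AE and Section 6.1.4 does not. Both are current text, and no order of precedence is given. This needs no interpretation.

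**2. Who loses data under footnote 13.** After the first dose, Table 3 schedules blood safety labs on Days 8, 29 and 36 and urinalysis on Days 8 and 36. The synopsis places the Day 29 sample before dosing. For a subject with no AE at exit, on nominal days:
- leaves before Day 8: no post-dose laboratory value;
- leaves from Day 8 to before Day 29: a Day 8 value and nothing later;
- leaves after the second dose and before Day 36: nothing after that dose;
- leaves after Day 36: has every laboratory value that a completer has.

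All of these subjects remain in the Safety Set, which needs only one administration (Protocol Section 8.2; SAP Section 2.1.1.2).

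**3. How many.** SAP Section 12 gives about 40 per group, so 5 × 40 = 200. Two rates are assumptions, not in the documents: 5–10% leave early, and 20–60% of leavers present with an AE.
- Leavers: 200 × 0.05 = 10 to 200 × 0.10 = 20.
- Leavers without exit labs: from 10 × (1 − 0.6) = 4 to 20 × (1 − 0.2) = 16.
- Per arm: 4/5 = 0.8 to 16/5 = 3.2.

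This is an upper range for those rates. It places every exit before Day 36 and assumes every leaver attends the visit, but a subject lost to follow-up gives no exit labs under either rule.

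**4. Effect of the selection.** Assume an abnormal laboratory value in 30% of leavers with an AE and 10% of those without.
- Rate seen under footnote 13: 30%.
- Rate among all leavers: 0.2 × 0.30 + 0.8 × 0.10 = 14%, to 0.6 × 0.30 + 0.4 × 0.10 = 22%.
- Abnormal values unseen: 4 × 0.10 = 0.4 to 16 × 0.10 = 1.6 subjects over all arms.

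If abnormal values were unrelated to AEs, the rate among leavers would not be distorted, but values would still be missing.

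**5. Footnote 7.** Two readings are possible.
- Literal: the visit applies to anyone who has not completed the study by 28 days from a dose. Completion is at Day 209, 180 days after the second dose, so the condition is always met and nobody is excluded.
- Restrictive: the visit applies only to exits within 28 days of a dose. With doses on Days 1 and 29 this covers Days 1 to 57, that is 57 − 1 = 56 of 209 − 1 = 208 follow-up days, leaving 152 (73%) outside. For a one-dose subject, 208 − 28 = 180 days (87%) fall outside. This reading conflicts with Section 6.1.4, which foresees later exits and gives them a complete examination. It also makes the 28-day condition in footnote 8 redundant.

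**The case against.** The strongest reply is that this is a footnote inconsistency with little effect on the primary endpoint. Much of that stands. AEs, SAEs and concomitant medications are marked at the early-termination visit without condition, so the dependence on outcome concerns three laboratory rows and not exit safety data in general. Leavers after Day 36 lose no laboratory value that completers have. The SAP does not say that early-termination values enter the maximum-shift table, so distortion there is possible but not established.

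A reader might infer several stronger claims that the documents do not support.

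- *That late leavers get no exit contact.* This rests on the restrictive reading of footnote 7, which footnote 8 and Section 6.1.4 speak against. Section 7.4 also provides for safety assessments on the withdrawal day and a visit 4 weeks after vaccination.
- *That the footnotes cause a 152-day gap in which SAEs are missed.* The interval from Day 57 to Day 209 has no scheduled contact for completers either. AE collection is planned only to its start ("Adverse events will be monitored continuously from first administration of IP treatment until study Day 57"), while Section 9.1 documents SAEs and medically attended events to Day 209. In SAP Section 9.2, events starting more than 30 days after the last dose (29 + 30 = Day 59) count as treatment-emergent only if related.
- *That Section 7.4 flatly contradicts footnote 13.* It asks for the relevant assessments of the withdrawal day, which need not include chemistry or hematology when none is due.

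Section 7.4 does not close the laboratory gap, however, because it does not list the content of its 4-week visit.

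**Conclusion.** The laboratory conflict between footnote 13 and Section 6.1.4 is real and should be resolved. Under Table 3, exit labs among leavers are selected on outcome, in a trial where one Grade 4 laboratory AE not clearly due to another cause suspends vaccination. The loss is confined to subjects without an AE who leave before Day 36. Their number is not in the documents; the range of 4 to 16 of about 200 is an upper range under assumed rates. Any effect on the primary endpoint is indirect, through laboratory AEs that are never observed. Footnote 7 is ambiguous rather than clearly restrictive, and needs rewording on either reading.

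**What to change.** Reconcile Table 3 footnotes 7, 8 and 13 with Sections 6.1.4 and 7.4, so that a single rule states who has the early-termination visit and which laboratory tests are taken there. Whichever rule the sponsor adopts, laboratory collection among leavers should not depend on whether an AE is present.

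In the SAP:
- report by arm the number of discontinued subjects with and without exit labs;
- state whether early-termination values enter the by-timepoint and maximum-shift summaries.

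The SAP postdates the end of enrollment, so samples not taken from subjects who left before Day 36 cannot be recovered. For those subjects the SAP additions are the useful part, with a note in the study report on which rule each site followed.

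The cost is a few footnote edits, laboratory fees for a few subjects, and one extra table. Table 3 already draws serum at this visit without condition, so no additional visit or venipuncture is needed.

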6.1.1. Screening Period 1 (Days -30 to Dosing)

In a private, individual setting, subjects will be given a full explanation of the nature of the study and written informed consent (IRB approval will be obtained before any study-related assessment) will be carried out. Group consenting will not be permitted and subjects requiring a Legally Authorized Representative may not participate in this study.

Screening for eligible and consenting subjects will be performed within approximately 30 days prior to randomization/IP administration.

Subjects may be consented and screened for serosusceptibility under a site-specific IRB-approved ICF.

At screening, subjects will be asked to attend the clinical site to have assessments performed as indicated in the Schedule of Events (Table 3).

All results from the screening procedure needed to evaluate eligibility, including the clinical laboratory results, must be available prior to study vaccination on Day 1. Any abnormal assessment at the screening visit will be assessed according to its clinical relevance, and if found clinically significant, the subject will not be included in the study.

During the screening period, the following procedures and assessments will be carried out for each subject to determine their eligibility for participation in the study:

- Obtain informed consent prior to any procedures being performed
- Record demographics
- Confirm eligibility criteria for enrollment and vaccination
- Obtain medical history
- Record concomitant medications
- Perform complete physical examination (neurological, rectal and gynecological exams do not need to be performed unless clinically indicated)
- Vital signs (height, weight, blood pressure, heart rate, and temperature)
- Collect urine for drug screen
- Collect urine for pregnancy test (applicable females only)
- Collect blood for serology for HIV, Hepatitis B & HCV
- Collect blood for serum chemistry and hematology
- Collect blood for immunogenicity assays
- Urinalysis (dipstick)
- Perform nasal swab
- Record any concomitant therapy/medically attended AEs/SAEs after signing of consent

Unscheduled visits may be planned to assess, confirm, and follow-up on out-of-range clinical laboratory test, or vital sign values that determine a subject's eligibility, or in case of a positive

urine drug screen. The result of the retest will be considered for subject eligibility. Findings made during unscheduled visits should be reported in the eCRF system.

A record of the number of screening failures and the reasons for screening failure will be captured in eCRF, but subjects who fail screening and are not enrolled will not otherwise be included in the database. The failure details will be documented in the subjects' study file.

6.1.2. Treatment Period (Day 1 to Day 57)

Assessments will be performed as indicated in the Schedule of Events ([Table 3](#)).

6.1.2.1. Day 1

- Update medical history
- Vital signs (blood pressure, heart rate, and temperature)
- Collect urine for pregnancy test (applicable females only)
- Collect blood for serum chemistry and hematology
- Urinalysis (dipstick)
- Review of inclusion and exclusion criteria
- Collect pre-dose blood sample for humoral immunogenicity assays (baseline MNT and other serum assays)
- Collect pre-dose blood sample (PBMC) for cellular immunogenicity assays (ELISpot) and/or innate transcriptome gene expression – select sites only
- Collect pre-dose blood sample (plasma) for cytokine expression – only if PBMC collected by site
- Perform limited physical examination
- Nasal swab into buffer for mucosal IgA and virus shedding
- Symptom Memory Aid (distribute and provide instructions, fill out form pre-dose to train subject on execution)
- Randomization
- Device weights (pre- and post-IP administration)
- IP administration
- Record concomitant therapy prior to dosing
- Record AEs/SAEs at 5 (+/- 1) and 30 (+/- 3) min after dosing

6.1.2.2. Day 4 ± 1 day

- Optional on-site visit for collection of blood sample (PBMC and plasma) for innate transcriptome gene expression – select sites only
- If subject does not attend on-site visit, scripted phone call with site to report symptoms (if unable to reach subject then email or SMS is acceptable)

- Record concomitant therapy/AEs/SAEs

6.1.2.3. Day 8 ± 1 day

- Perform limited physical examination
- Vital signs (blood pressure, heart rate, and temperature)
- Collect blood for serum chemistry and hematology
- Urinalysis (dipstick)
- Symptom Memory Aid reviewed
- Nasal swab into buffer for mucosal IgA and virus shedding
- Collect blood sample for humoral immunogenicity assays (MNT and other serum assays)
- Collect blood sample (PBMC) for cellular immunogenicity assays (ELISpot) and/or innate transcriptome gene expression – select sites only
- Collect blood sample (plasma) for cytokine expression – only if PBMC collected by site
- Record concomitant therapy/AEs/SAEs

6.1.2.4. Day 29 ± 7 days

- Confirm eligibility for second vaccination
- Update medical history
- Vital signs (blood pressure, heart rate, and temperature)
- Collect urine pre-dose for pregnancy test (applicable females only)
- Collect blood for serum chemistry and hematology
- Perform limited physical examination
- Nasal swab into buffer for mucosal IgA and virus shedding
- Collect pre-dose blood sample for humoral immunogenicity assays (MNT and other serum assays)
- Collect pre-dose blood sample (PBMC) for cellular immunogenicity assays (ELISpot) – only by select sites
- Collect pre-dose blood sample (plasma) for cytokine expression – only if PBMC collected by site
- Symptom Memory Aid (distribute and provide instructions)
- IP administration
- Device weights (pre- and post-IP administration)
- Record concomitant therapy/AEs/SAEs prior to dosing and at 5 (+/- 1) and 30 (+/- 3) min after dosing

